Sample Size and Power analysis: Based on our previous study of nurse coaching using MI to improve disease self-management (23), we found improvement in self-efficacy scores significantly higher in the intervention group compared to the control group. Based on these data, we expect to find self-efficacy scores to be 4.03 and 3.64, for the intervention and control group respectively, with a standard deviation of 0.70. Table 1 presents the sample size calculations for the number of eligible patients needed to detect significant differences in self-efficacy scores between the cohorts.

According to the anticipated enrollment calculations above, we expect to enroll at least 150 patients in each of the intervention and control cohorts. This sample size will be sufficient to detect differences between the two groups as demonstrated in Table 1. In the previous study, we had a low overall attrition rate of 16% using a similar intervention design with comparable demand on participants for time and response. Even under the conservative assumption that design effects and dropout rates may result in a reduced sample size of 100 per treatment group, our study will still have at

Patient and Provider Engagement and Empowerment through Technology $(P^2E^2T^2)$ to Improve Health in Diabetes

least 80% power to detect the specified clinically important effect size. We will not enroll more than 350 participants in total.

Difference in Self- Efficacy Scores	Significance Level (Alpha)	Power (1-Beta)	Intervention, N	Control, N
0.20	0.05	0.80	219	219
0.25	0.05	0.80	134	134
0.30	0.05	0.80	92	92
0.35	0.05	0.80	67	67
0.40	0.05	0.80	51	51

8) Recruitment Methods

We propose several approaches to accomplish our recruitment goals within the time frame of the funded study. These will be used in concert with one another to achieve the full sample.

Potential study participants will be identified by a query of the Electronic Health Record (EHR) at UC Davis Health System for specific elements essential for eligibility (over age 18; assignment to one of the participating primary care clinics & providers; diagnosis of Diabetes Mellitus-Type 2; and HgbA1C value of over 6.5 %). Affiliated clinic providers will be notified in advance that eligible patients from their census will be contacted for study participation.

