9) Compensation to the Subjects

All subjects, regardless of treatment arm, will be given a health monitoring device at the end of the study. Upon completion of study questionnaire and their regularly scheduled visit with their primary care physician all participants will receive \$50 at baseline, 3 and 9 months. Those participants in the intervention $(P^2E^2T^2)$ arm will receive a health monitoring device at the beginning of the study; and those participants in the Care Coordination arm of the study will also receive a health monitoring device upon successful completion of all study questionnaires. If participants do not complete all aspects of the study, they will not receive the health monitoring sensor device. Each sensor device is worth approximately \$75.

10) Study Timelines

Each individual will be enrolled in the study for 9 months. Each participant will complete a study questionnaire at baseline, 3 months and 9 months. Estimated duration of the study completion is 24 months from start of enrollment (January 1^{st} , 2016 – December 31^{st} , 2017).

11) Study Endpoints

Outcomes to be evaluated include: i) Quality of Life (QOL) measures; ii) Self-efficacy; iii) Readiness to Change; and iv) Clinically Relevant Indicators (HgbA1C, HDL, LDL, triglycerides). All measures will be collected in both groups at the study timelines. At baseline (time of recruitment), all participants will be asked to complete the surveys and the care coordinator will request the primary care provider orders for the laboratory tests measuring the clinical indicators. The lab tests are routinely used to monitor diabetes management and are typically covered by insurance. Should the patient not have a payment source for the laboratory assays, the project will cover the cost of the laboratory tests. At 3 months and 9 months, surveys links will be sent by email to each participant along with a reminder to complete the laboratory work ordered by their provider. If not completed, reminder emails or phone calls may be made by the study team. The primary endpoints of the study are: baseline data; data at the completion of five sessions of support calls during the 3 months of the intervention; and data at 6 months after the end of the intervention (9 months after baseline).

12) **Procedures Involved**

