Patient and Provider Engagement and Empowerment Through Technology Program to Improve Health in Diabetes

PI: [name]

January 11, 2019

NCT number: NCT02672176

Analytical and Statistical approaches

We will use Stata v15.0 (Stata Corp, College Stations Tx 2017) for all statistical analyses. Descriptive analysis will yield means/standard deviations for continuous variables and frequencies for categorical variables. We will examine distributions to determine whether data meets assumptions for planned statistical analyses. We will compare patient demographic and health-related characteristics between the individuals in the intervention group and the usual care group. We will compare continuous variables using a Student's t test or the Wilcoxon Signed-Rank test, and will compare categorical variables using the chi-squared test and Fisher's exact test, as appropriate. We will compare number of steps per week at baseline (Week 2) versus 3 months (Week 13), baseline versus 9 months (Week 37) and 3 months versus 9 months, using a paired t-test to evaluate the change in physical activity over time.

We will calculate change in outcomes over time as the difference between baseline and 3 months, and baseline and 9 months for diabetes self-efficacy scores, depression severity (PHQ-9), patient stress score, and PROMIS measures (Emotional distress anxiety, and physical functioning). We will use Student's t test to compare the change in outcome between usual care and intervention groups (Significance level: $p \le .05$).

In the primary analysis, we will estimate the difference over time in the effects of the intervention over usual care in the study participants. This is an intent to treat analysis, with the assumption that any dropouts are missing at random. We will also use an analytical method (Mixed model) which accounts for the missing data contributed by participants who dropped out from the study. Lastly, we will conduct a sensitivity analysis to determine whether there is a difference with regards to the significance of our findings when we exclude participants who drop out from the analysis. All participants, regardless of intervention completion, will be included in the intent to treat analysis.

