We will use multivariate regression modeling for all hypotheses testing to estimate withingroups and across group effects of the intervention on the outcome (significance level: $p \le$ 0.05). The mixed effects models will evaluate the impact of the intervention over time in the outcomes of Diabetes Self-Efficacy, depressive symptoms, and Perceived Stress Score (PSS). We will include a binary indicator for intervention group assignment, and a group- by-time interaction term in the models to compare improvement over time between the intervention group and usual care group. We will assess all variables for collinearity before including in the model. We will evaluate model fit using deviance tests for nested models, the Akaike Information Criterion, and the Bayesian Information Criterion for non-nested models. We will assess the estimates for the fixed effects using a pre-determined significance level (p < 0.05) on two sided tests and 95% confidence intervals. We will use the same approach for analyzing primary and secondary outcomes analyzing the effect of the intervention at baseline, 3 and 9 months.

We will conduct a post-hoc analysis examining the relationship between stage of change at baseline and intervention outcomes. We hypothesize that there might be differences in who the intervention benefits most – and will explores whether readiness to change status might be a tool for screening potential participants for inclusion in future trials or interventions.

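### The between-arm analyses use raw change and a mixed model with unconstrained baseline means; baseline adjustment, which neither document specifies, would gain precision and remove a mismatch with the apparent power basis.

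*SAP*

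**What the plan says.** The SAP (Analytical and Statistical approaches) defines the outcome variable for its simple comparison as a plain subtraction: "We will calculate change in outcomes over time as the difference between baseline and 3 months, and baseline and 9 months". It then says "We will use Student's t test to compare the change in outcome between usual care and intervention groups".

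For the mixed models it says "We will include a binary indicator for intervention group assignment, and a group- by-time interaction term in the models", and it describes the approach as "analyzing the effect of the intervention at baseline, 3 and 9 months". Baseline is therefore one of the modelled visits, and the arm indicator leaves the two arms free to have different baseline means. The SAP lists no further covariates. It says only "We will assess all variables for collinearity before including in the model".

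The baseline value is available for adjustment. Protocol section 10 states "Each participant will complete a study questionnaire at baseline, 3 months and 9 months".

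On power, Protocol section 7 says "we expect to find self-efficacy scores to be 4.03 and 3.64, for the intervention and control group respectively, with a standard deviation of 0.70". The sample-size table in that section (Table 1) is indexed by the difference in self-efficacy scores. No SD of change and no correlation between visits is given.

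**The concern.** Under randomization, subtracting the baseline is a valid way to compare arms, but it is not the most precise one. Subtraction fixes the weight on the baseline score at 1. Regression uses the weight that the data support, which is rho when visit variances are equal. For any rho below 1, fixing the weight at 1 costs precision. A mixed model with free baseline means does not recover the loss, because its group-by-time contrast estimates the same difference in mean change.

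There is also a question of consistency. If the SD of 0.70 describes scores at one visit, section 7 powers a comparison of score levels while the SAP tests changes. The SD of a change is larger or smaller than 0.70 depending on a correlation that the plan does not state. At stake are the width of the confidence intervals and whether the stated power describes the planned test.

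**Working it through.** **Inputs.** Difference 4.03 − 3.64 = 0.39 and SD 0.70; Table 1 differences, including 0.30; at least 150 per arm planned and a reduced figure of 100 per arm (all Protocol section 7). Two-sided 5% level (SAP). rho is not in the documents, so 0 to 0.7 is assumed.

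**Step 1: the plan's own figures.** With SD 0.70, two-sided alpha 0.05 and 80% power, the two-sample t formula gives 194, 125, 87, 64 and 50 per arm for differences 0.20, 0.25, 0.30, 0.35 and 0.40. Table 1 gives 219, 134, 92, 67 and 51. The table is larger in every row and no single SD fits it (the implied SD falls from 0.747 to 0.721), so it errs on the conservative side; that is a separate matter. The text's claim of at least 80% power at 100 per arm holds for 0.39 on score levels: power is 97.5%.

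**Step 2: formulas (equal visit variances).**
- SD of change = 0.70 × sqrt(2(1 − rho))
- Residual SD with baseline adjustment = 0.70 × sqrt(1 − rho²)
- Variance ratio, adjusted to change = (1 − rho²) / (2(1 − rho)) = (1 + rho)/2

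The SD of change exceeds 0.70 when 2(1 − rho) > 1, that is, when rho < 0.5. The adjusted SD never exceeds 0.70.

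**Step 3: does the mixed model behave like the t test?** Generalized least squares variances of the arm contrast at a follow-up visit, for three visits, categorical time, equal correlation, complete data and 100 per arm:

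| rho | Raw change | Mixed model, free baseline | Mixed model, common baseline | ANCOVA | Ratio |
|---|---|---|---|---|---|
| 0.3 | 0.01372 | 0.01372 | 0.00892 | 0.00892 | 0.65 |
| 0.5 | 0.00980 | 0.00980 | 0.00735 | 0.00735 | 0.75 |
| 0.7 | 0.00588 | 0.00588 | 0.00500 | 0.00500 | 0.85 |

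As an example at rho 0.5: raw change is 2 × 0.49 × 2(0.5)/100 = 0.0098; ANCOVA is 2 × 0.49 × 0.75/100 = 0.00735. Under these conditions the mixed model with an arm indicator matches the raw-change comparison, and the common-baseline model matches ANCOVA.

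**Step 4: power at 100 per arm for a 0.30 difference** (two-sided noncentral t; adjusted power uses the residual SD and ignores the one degree of freedom spent on the covariate).

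| rho | SD change | SD adjusted | Power, change | Power, adjusted |
|---|---|---|---|---|
| 0.2 | 0.885 | 0.686 | 66.4% | 86.8% |
| 0.3 | 0.828 | 0.668 | 72.2% | 88.5% |
| 0.4 | 0.767 | 0.642 | 78.6% | 90.8% |
| 0.5 | 0.700 | 0.606 | 85.4% | 93.6% |
| 0.7 | 0.542 | 0.500 | 97.3% | 98.8% |

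The change score reaches 80% at rho of about 0.42.

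**Step 5: power at 100 per arm for the expected 0.39.** Change score: 79.2%, 87.3%, 91.2% and 97.5% at rho 0, 0.2, 0.3 and 0.5. Adjusted: 97.5%, 97.9%, 98.4% and 99.5%.

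**The case against.** **Power is ample where it matters.** The expected difference is 0.39, and 100 per arm is the protocol's own conservative floor. At 150 per arm, change-score power for 0.30 is 83% even at rho 0.2. At 126 per arm (150 × 0.84, using the 16% attrition in section 7) it is 76% at rho 0.2 and 82% at rho 0.3. Above rho 0.5 the change score beats the SD used for power. This stands.

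**The SD of 0.70 is not labelled.** Section 7 speaks of improvement in scores just before giving the figure. The two means beside it look like score levels, which is the likelier reading. If 0.70 were an SD of change, the mismatch with the power basis would go, but the loss against baseline adjustment would remain.

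**Baseline adjustment is unstated, not excluded.** Baseline does enter, by subtraction and as a modelled visit, and the covariate list is open. The SAP does not say whether time is categorical, and it expects dropout, so the equality in Step 3 will not be exact in practice. This stands as a limit on the claim.

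**The t test may not be the main test.** The SAP introduces its primary analysis after the t test and assigns hypothesis testing to regression models. That does not remove the point, since the mixed model as described shares the loss.

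**Adjustment is not a general cure for reporting bias.** Protocol section 29 places the initial surveys after randomization. If knowing the arm shifts baseline answers alone by s, the change score carries the whole shift and ANCOVA about rho × s. If the same shift persists at follow-up, the change score cancels it and ANCOVA is off by (1 − rho) × s. The case for adjustment here is therefore precision, and it needs a stated assumption about the baseline answers.

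**Conclusion.** The point holds as one of efficiency and consistency. With complete data, categorical time and equal visit variances, both planned between-arm analyses have 15% to 35% more variance to shed: adjustment removes 35%, 25% and 15% of it at assumed rho of 0.3, 0.5 and 0.7. If 0.70 is a score SD, the stated power refers to a different quantity from the one tested, and for a 0.30 difference at 100 per arm the 80% level depends on rho being about 0.42 or more. With adjustment it does not depend on rho.

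A reader might infer that the trial is underpowered. The documents do not support that: for the expected 0.39 difference at 100 per arm, change-score power is 79% at rho 0 and 87% or more from rho 0.2. A reader might also infer that the change-score comparison is biased, or that the SAP forbids baseline adjustment. Neither follows. The comparison is valid under randomization, and the covariate list is simply not given. The change is recommended rather than essential.

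**What to change.** In the SAP, make a baseline-adjusted estimate the between-arm analysis at 3 and 9 months. Name one of two forms: ANCOVA on the follow-up score with the baseline score as covariate, or a mixed model with categorical time, arm effects at 3 and 9 months, and baseline means common to both arms (no arm main effect). Keep the change-score t test as supportive.

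State that baseline answers are assumed unaffected by knowledge of the arm, because the surveys follow randomization; both forms rest on this. State also whether 0.70 is the SD of a score or of a change.

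The cost is wording only: the baseline scores are already collected and no more participants are needed. Timing does matter. The SAP is dated January 2019, and Protocol section 10 plans completion by December 2017. If outcome data had been seen by arm when the change is made, label the adjusted analysis as a later change and report the original comparison beside it.

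### The SAP points to the mixed model but names neither the deciding visit nor the time contrast, and it keeps a parallel between-arm t-test at 0.05

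*SAP*

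**What the plan says.** All of this is in the SAP's single section, Analytical and Statistical approaches.

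- **Change-score t-test (second paragraph).** "We will calculate change in outcomes over time as the difference between baseline and 3 months, and baseline and 9 months" is the definition, applied to self-efficacy, PHQ-9, stress and two PROMIS scores. Arms are then compared by a Student's "t test to compare the change in outcome between usual care and intervention groups", and that sentence carries its own 0.05 level.
- **Primary analysis (third paragraph).** It concerns the difference over time between arms, and no test or visit is named. "This is an intent to treat analysis, with the assumption that any dropouts are missing at random". Then: "We will also use an analytical method (Mixed model) which accounts for the missing data contributed by participants who dropped out from the study". Also: "All participants, regardless of intervention completion, will be included in the intent to treat analysis".
- **Regression (fourth paragraph).** "We will use multivariate regression modeling for all hypotheses testing". Mixed models are specified for self-efficacy, depressive symptoms and perceived stress, with a group indicator and a group-by-time "interaction term in the models to compare improvement over time", two-sided at 0.05. The paragraph closes by extending the approach to primary and secondary outcomes at baseline, 3 and 9 months.

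The protocol (Number of Subjects) bases its sample size on self-efficacy of 4.03 versus 3.64 with SD 0.70, and names no visit for that difference.

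**The concern.** Self-efficacy, depression and stress are each compared between arms by two methods, each with a 0.05 level, and the t-test is run at two visits. Nothing says what follows if 3 and 9 months disagree, or if the t-test and the model disagree. The model's own contrast is also open. A group-by-time term could give one effect per visit, one joint test over both visits, or one linear slope, and these answer different questions.

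At stake is whether a single significant result among several could be presented as the trial's finding. The SAP is dated 11 January 2019, and the protocol (Study Timelines) estimated completion by 31 December 2017. The documents do not say whether results by arm had been seen, so an explicit rule is worth having.

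**Working it through.** **Inputs from the documents.** 150 per arm; 16% attrition in the previous study; SD 0.70; planned difference 4.03 − 3.64 = 0.39 (all protocol, Number of Subjects). Visits at 0, 3 and 9 months. Retained per arm: 150 × 0.84 = 126.

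**Assumed, not in the documents.** Equal variances and the same within-patient correlation r between any two visits, with r = 0.3, 0.5, 0.7.

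**The plan's own figure.** The only related figure is at least 80% power at 100 per arm. For 0.39: Φ(0.39 / (0.70 × √(2/100)) − 1.96) = Φ(1.98) = 97.6%. That statement holds.

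**1. Two visits, one outcome, no true effect.**
- Changes from baseline: the covariance of the 3- and 9-month changes is σ²(1 − r) and each variance is 2σ²(1 − r), so their correlation is 0.5 whatever r is. For two standard normals with that correlation, the chance that at least one exceeds 1.96 in absolute value is 9.1%.
- Baseline-adjusted contrasts: the correlation is (r − r²)/(1 − r²) = r/(1 + r) = 0.23, 0.33, 0.41, giving 9.6%, 9.5%, 9.3%.
- Upper reference, if independent: 1 − 0.95² = 9.75%.
- Simulation (10,000 trials per setting; 8% lost before 3 months and 8% of those randomised lost between 3 and 9; dropout depending on the last observed value with an assumed log-odds slope of 0.75 per SD, same in both arms): mixed model at either visit, 9.0–9.2%. At a single visit it holds 4.6–5.1%.

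**2. What the second method adds.** With free baseline means, visit-specific time and complete data, the model's contrast equals the difference in mean changes, so the two tests part only through dropout. In the same simulation, t-test or model significant at 9 months: 6.2%, 5.9%, 5.8% for r = 0.3, 0.5, 0.7, about 1 point above 5%. Over both visits, any of the four results: 11.0%, 10.6%, 10.4%, against 9.0%, 9.2%, 9.2% for the model alone. If the model constrains baseline means to be equal, it agrees less with the change score. A separate simulation of 4,000 trials per setting then gave 12.7–15.2% for any of four, against 8.9–10.0% for the model at either visit.

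**3. Time coding.** Suppose the true arm difference is 0 at baseline and 0.39 at both later visits. The mean of 0, 3, 9 is 4; deviations are −4, −1, 5; their sum of squares is 16 + 1 + 25 = 42. The linear interaction is (5 × 0.39 − 1 × 0.39)/42 = 0.0371 per month. The estimated difference in change is 3 × 0.0371 = 0.11 at 3 months and 9 × 0.0371 = 0.33 at 9. These are interaction contrasts. Adding the group term gives fitted arm differences of 0.26 − 0.037 = 0.22 and 0.26 + 5 × 0.0371 = 0.45, which are not 0.39 either.

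**4. Value of baseline adjustment.** Change SD = 0.70√(2(1 − r)); adjusted SD = 0.70√(1 − r²); variance ratio = (1 + r)/2. Half-width = 1.96 × SD × √(2/126).

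| r | Variance ratio | Change-score half-width | Adjusted half-width |
|---|---|---|---|
| 0.3 | 0.65 | 0.20 | 0.16 |
| 0.5 | 0.75 | 0.17 | 0.15 |
| 0.7 | 0.85 | 0.13 | 0.12 |

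**The case against.** The best defence is that the method is already chosen. Regression is named for every hypothesis test. The t-test sits before the paragraph on the primary analysis, and that paragraph's intent-to-treat and missing-at-random wording fits a mixed model rather than a t-test on those with follow-up. This largely stands. A reader might infer that the SAP has two rival primary methods, but the text does not support that. What remains is that the model is introduced as an addition and the t-test keeps its own significance level, so one clarifying sentence is needed.

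The defence can also say that no passage lets any one significant result count as success, and that a joint two-degree-of-freedom interaction test would hold 5% across both visits. Both are true. The 9% is therefore conditional, and it is not the trial's error rate. But the SAP does not choose the joint test either.

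Four further inferences go beyond the documents:
- *That the protocol's Study Endpoints section sets up competing primary visits.* Its list includes baseline, on which no effect can be claimed, so it reads as a list of data-collection points.
- *That the SAP's date shows the results were known.* The completion date is an estimate, and nothing is said about access to data.
- *That the t-test is invalid because it omits people without follow-up.* Under the same dropout mechanism in both arms its simulated error was 4.8–5.2%. With selective dropout in one arm only it was 5.1–6.2%, with bias of 0.01–0.03 points.
- *That the check excluding dropouts is defective.* It is limited but legitimate.

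**Conclusion.** The point holds in a limited form. The mixed model is the indicated method, but the deciding visit and the time contrast are not fixed, and the t-tests are not labelled as secondary. Type I error for one outcome would be about 9% if either visit could count, under visit-specific contrasts and the assumed r of 0.3 to 0.7. Duplication of method is the smaller part, about 1 point at a visit with free baseline means. It grows if baseline is adjusted for and the t-tests keep their status, so the two changes belong together. Linear coding would misstate an effect that is already complete at 3 months. The precision gain from baseline adjustment rests on the same assumed r and on equal variances. Sample size and stated power are unaffected. This should be fixed, but it does not undermine the design.

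**What to change.** State in the SAP that:

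1. The deciding analysis is the likelihood-based mixed model on all randomised participants, with time as a category (0, 3, 9 months), group-by-time terms, and baseline adjusted for, either as a covariate or by constraining baseline means to be equal.
2. One visit decides, or one joint two-degree-of-freedom group-by-time test does. If results by arm had already been seen, label this choice post hoc.
3. Both visit differences are reported with 95% confidence intervals.
4. The change-score t-tests are descriptive.
5. The model with free baseline means is reported as a check, because the initial surveys are given after randomisation (protocol, Consent Process).

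Minor and separate: the first paragraph of the SAP names the Wilcoxon signed-rank test, a paired test, for comparing characteristics between independent arms. The rank-sum test is the one needed.

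The cost is a few sentences and modest extra work in the Stata package already planned, with no new data. The downside is that, if one visit is named, an effect seen only at the other visit would be supportive rather than confirmatory.
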